16.2. APPENDIX 2: TUBERCULOSIS SCREENING

All participants must undergo screening for a history of tuberculosis (TB) infection and testing for latent/active TB infection. Their medical history review must include specific questions about a history of TB or known occupational or other personal exposure to individuals with active TB. Participants should be asked about past testing for TB, including chest radiograph results and results of interferon-gamma release assay (IGRA, eg, QuantiFERON-TB Gold In-Tube, T-SPOT TB) or response to tuberculin skin test (TST) and history of Bacillus Calmette-Guérin vaccination.

- a. Participants without a history of latent or active TB who have a negative IGRA or TST result at screening are eligible to enroll in the study.
- b. A TB questionnaire will be completed for all participants (refer to questionnaire below) during the Screening period.
- c. For participants who are receiving TB prophylaxis treatment the TB questionnaire will be completed at every study visit (until TB prophylaxis treatment course is completed). This questionnaire will monitor for any emergent symptoms of active TB and compliance with any TB prophylaxis treatment.
- d. The IGRA or TST is NOT required at screening (or annually) for participants with a history of active/latent TB infection.
 - Participants with past or current history of active TB, regardless of treatment history, are excluded from enrollment.
 - Participants with a history of latent TB infection diagnosed prior to screening must have documentation of treatment with at least four weeks of an acceptable TB prophylaxis treatment regimen to qualify for enrollment. It is the responsibility of the investigator to verify the adequacy of previous TB treatment and provide appropriate documentation (Direct Observation Therapy report where available).
- e. Acceptable TB prophylaxis treatment regimens for latent TB is defined according to local country guidelines. If no local country guidelines for the treatment of latent TB exist, WHO guidelines must be followed.
- f. Participants with a newly identified positive IGRA (one retest is allowed with approval from the Medical Monitor per Section 9.3.2) or TST result at Screening must be considered a Screen Failure, however they are eligible for rescreening once they undergo an evaluation to rule out active TB (chest X-ray to rule out pulmonary TB) and initiate an acceptable TB prophylaxis treatment regimen for latent TB at least 4 weeks prior to rescreening (with a plan to complete the TB treatment course during study participation) before they can be considered for enrollment.
- g. An assessment of adequacy of the TB prophylaxis treatment regimen and duration of treatment must be performed by an infectious disease consultant or physician TB expert.
- h. IGRA and TST interpretation
 - Participants will be considered to have a negative diagnostic test for TB if at least one of the following circumstances applies:
 - Negative IGRA.
 - Combination of a negative IGRA and negative purified protein derivative (PPD) TST (in countries where IGRA is not considered a validated test).

- A combination of two intermediate/indeterminant IGAs and a negative PPD TST. An intermediate/indeterminant IGRA test result should be repeated. In the event that the second IGRA test result is also intermediate/indeterminate, the participant may be enrolled without treatment for latent TB if his/her chest radiograph shows no abnormality suggestive of TB (active or old, inactive TB) and the participant has no additional risk factors for TB as determined by a physician TB expert physician.
- If the IGRA is not considered a validated test or is not registered for use in the participant's country, a negative TST result is required to rule out latent TB infection.
- A positive TST reaction is ≥ 10 mm of induration, or ≥ 5 mm of induration for participants receiving equivalent of prednisone > 15 mg/day for any medical conditions.

- i. Resources
 - For the WHO guidelines for the treatment of latent TB visit:
https://apps.who.int/iris/bitstream/handle/10665/44165/9789241547833_eng.pdf;jsessionid=115F807C3008D688F75118AF16EA53F0?sequence=1

Tuberculosis Screening Questionnaire

Etrasimod Program
Tuberculosis Screening Questionnaire
Created by Arena Pharmaceuticals, Inc.
Version 1.0, 17Jan2020

Site #: _____
Subject #: _____

Tuberculosis Screening Questionnaire Source Document Worksheet

Instructions:

1. This source document worksheet should be completed by the PI or delegated site staff.
2. This source document worksheet should NOT be given to the subject for completion.
3. Please complete for ALL subjects during the Screening visit.
4. Please complete at every study visits for subjects who are receiving TB prophylaxis treatment (until the TB prophylaxis treatment course is completed) and at designated post-baseline study visits (per protocol schedule of assessments) for subjects who reside in countries with a high burden of TB or multi-drug resistant (MDR) TB as identified by WHO. The current WHO TB high burden country (HBC) and MDR TB HBC lists can be found at the following URL:
<http://www.stoptb.org/countries/tbdata.asp>.
5. Enter all applicable information on the corresponding eCRF.

Was the Tuberculosis Screening questionnaire completed? Yes/No

If yes, please enter completion date (DD/MM/YYYY): _____

If no, specify reason:

Date of completion of TB Screening Questionnaire, if applicable: _____

Study Visit Number: _____

Section 1: Questions to ask the subject

*Time frame: in the past year or since your last study visit.

1. Have you experienced any of the following symptoms ?*	
a) A productive cough (coughing up phlegm) for more than 3 weeks	Yes / No
b) Hemoptysis (coughing up blood)	Yes / No
c) Unexplained weight loss	Yes / No
d) Fever, chills, or night sweats for no known reason	Yes / No
e) Persistent shortness of breath (difficulty breathing)	Yes / No
f) Unexplained fatigue	Yes / No
g) Chest pain	Yes / No

Erasimod Program
Tuberculosis Screening Questionnaire
Created by Arena Pharmaceuticals, Inc.
Version 1.0, 17Jan2020

Site #: _____
Subject #: _____

2. Have you had contact with anyone with active tuberculosis disease ?*	Yes / No
3. Have you been diagnosed with latent TB infection?	Yes / No
a) If yes, list medication(s) used to treat latent TB infection and treatment dates (please ensure listed on Concomitant Medication Source Log and eCRF, as applicable).	
Medication #1: _____ Start date of Medication #1: _____ Expected stop date of Medication #1: _____ Have you missed taking any doses of Medication #1? Dates of Missed Doses: _____ # of Missed Doses: _____	Yes / No
Medication #2: _____ Start date of Medication #2: _____ Expected stop date of Medication #2: _____ Have you missed taking any doses of Medication #2? Dates of Missed Doses: _____ # of Missed Doses: _____	Yes / No
Medication #3: _____ Start date of Medication #3: _____ Expected stop date of Medication #3: _____ Have you missed taking any doses of Medication #3? Dates of Missed Doses: _____ # of Missed Doses: _____	Yes / No
Medication #4: _____ Start date of Medication #4: _____ Expected stop date of Medication #: _____ Have you missed taking any doses of Medication #4? Dates of Missed Doses: _____ # of Missed Doses: _____	Yes / No

Please provide details to any question answered "Yes."

Erasimod Program
Tuberculosis Screening Questionnaire
Created by Arena Pharmaceuticals, Inc.
Version 1.0, 17Jan2020

Site #: _____
Subject #: _____

Section 2: To be completed by the investigator

I. The participant is on concomitant medication(s) with immunosuppressive effects: Yes / No

If yes, specify medication(s) (name, dosage):

Medication #1:

Medication #2:

Medication #3:

Medication #4:

II. TB QuantiFERON or Tuberculin Skin Test result: _____ Date: _____

Chest x-ray/computer tomography (CT) scan done to rule out pulmonary TB? Yes / No

If yes, date of chest x-ray or CT scan: _____

Any evidence of active pulmonary TB disease on chest x-ray or CT scan? Yes / No

Other assessment completed? Yes / No

If yes, specify assessment: _____

If yes, date of other assessment: _____

Any evidence of active TB disease on assessment? Yes / No

III. Upon review of the responses and discussion with the participant, I recommend the following:

Perform screening test for latent TB infection

Perform additional assessments to rule out active TB disease

Refer to physician TB expert for evaluation and treatment

Follow up at the next TB-designated study visit and repeat TB screening questionnaire

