4.2. Exclusion Criteria

Participants who meet any of the following exclusion criteria will not be eligible for enrollment into the study:

Exclusions related to general health:

1. Severe extensive colitis as evidenced by:
 - Physician judgment that the participant is likely to require hospitalization for medical care or surgical intervention of any kind for UC (eg, colectomy) within 12 weeks following randomization
 - Current evidence of fulminant colitis, toxic megacolon or recent history (within last 6 months) of toxic megacolon, or bowel perforation
 - Previous total or partial colectomy
2. Diagnosis of CD or indeterminate colitis or the presence or history of a fistula consistent with CD
3. Diagnosis of isolated proctitis (defined as proctitis with < 10 cm rectal involvement), microscopic colitis, ischemic colitis, or infectious colitis
4. Hospitalization for exacerbation of UC requiring IV steroids within 12 weeks of screening (a single dose of IV steroids given is acceptable)
5. Positive assay or stool culture for pathogens (ova and parasite examination, bacteria) or positive test for *Clostridioides difficile* toxin at screening (If *C. difficile* is positive, the participant may be treated and retested \geq 4 weeks after completing treatment.)
6. Pregnancy, lactation, or a positive serum beta-human chorionic gonadotropin (β -hCG) measured during screening
7. Clinically relevant neurological, endocrine, metabolic (including, but not limited to, hypo- and hyperkalemia), psychiatric, cognitive impairment, alcohol/drug abuse/dependence, or other major

systemic disease making implementation of the protocol or interpretation of the study difficult or would put the participant at risk

8. Have any of the following conditions or receiving treatments that may affect cardiovascular function:
 - Myocardial infarction, unstable angina, stroke/transient ischemic attack, decompensated heart failure requiring hospitalization or Class III/IV heart failure \leq 6 months prior to or during the screening period
 - History or presence of second-degree or third-degree AV block, sick sinus syndrome, or periods of asystole for $>$ 3 seconds without a functional pacemaker
 - History or presence of recurrent symptomatic bradycardia or recurrent cardiogenic syncope

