 - Screening or Week 0/Day 1 pre-randomization vital signs (taken in the sitting position) with a HR $<$ 50 bpm OR systolic blood pressure (BP) $<$ 90 mm Hg OR diastolic BP $<$ 55 mm Hg. Vital signs may be repeated up to 3 times during a visit to confirm abnormal readings
 - Screening or Week 0/Day 1 pre-randomization ECG with PR interval $>$ 200 ms or Fridericia's corrected QT interval (QTcF) \geq 450 ms in men or \geq 470 ms in women
 - Start, stop, change or planned change in dosage of any anti-arrhythmic drugs (Class I to IV) \leq 1 week before screening or within 1 week before or after randomization
9. Forced expiratory volume at 1 second (FEV₁) or forced vital capacity (FVC) $<$ 70% of predicted values and FEV₁/FVC ratio $<$ 0.70 at screening
10. Uncontrolled diabetes as determined by hemoglobin A1c (HbA1c) $>$ 9% at screening, or participants with diabetes with significant comorbid conditions such as retinopathy
11. History of macular edema or retinopathy
12. History of active tuberculosis (TB), history of untreated or inadequately treated latent TB infection, active or latent TB infection at screening (refer to [Appendix 2](#) for details on TB screening requirements and interpretation of test results). The following are EXCEPTIONS to this exclusion criterion:
 - Participants with latent TB, who have been ruled out for active TB, have completed an appropriate course of TB prophylaxis treatment per national/local medical guidelines or WHO guidelines, have a chest radiograph without changes suggestive of active TB infection, and have not had recent close contact with a person with active TB are eligible to enroll in the study. It is the responsibility of the Investigator to verify the adequacy of previous TB treatment and provide appropriate documentation of treatment compliance
 - Participants diagnosed with latent TB at screening, ruled out for active TB and received at least 4 weeks of an appropriate TB prophylaxis regimen may be rescreened for enrollment. Participants will complete their prophylactic regimen during the trial
13. A clinically significant active infection (eg, serious and/or atypical) \leq 28 days prior to randomization, required IV medication \leq 14 days prior to randomization, or that may worsen (in

the opinion of the Investigator) if the participant is treated with a drug having immunosuppressant effects (ie, etrasimod). Fungal infection of nail beds is allowed.

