9. STUDY ASSESSMENTS AND PROCEDURES

9.1. General Instructions

- Study procedures and their timing are summarized in the Schedule of Assessments ([Table 6](#)). Protocol waivers or exemptions are not allowed.
- Results of all protocol-required procedures will be recorded in the eCRF whenever applicable.
- Immediate safety concerns should be discussed with the Medical Monitor immediately upon occurrence or awareness to determine if the participant should continue or discontinue study treatment.
- Adherence to the study design requirements, including those specified in the Schedule of Assessments ([Table 6](#)), is essential and required for study conduct.
- Study visits should be scheduled in the morning, whenever possible.

- All laboratory assessments required by the protocol will be performed by a central laboratory unless otherwise stated.
- For onsite and offsite study visits (refer to Section 9.6 and [Table 6](#)), participants should take their study treatment after blood draws for PK and after all pre-dose assessments and procedures have been completed.

The Investigator will maintain a screening log and enrollment log to record details of all participants screened and to confirm eligibility or record reasons for screening failure, as applicable.

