9.3. Screening and Eligibility

Participant eligibility will be assessed based on protocol inclusion and exclusion criteria. All screening evaluations must be completed and reviewed to confirm potential participants meet all eligibility criteria.

Screening procedures must be completed within 28 days prior to receiving the first dose of study treatment ([Table 6](#)). The Screening Period may be extended for participants who require additional diagnostic testing/consults to determine status of either latent TB or *C. difficile* infection. If the participant is planned to be randomized > 28 days from the signing of the informed consent form (ICF), the Medical Monitor should be consulted to see if repeated testing is needed. The 28-Day Screening Period may also be extended on a case-by-case basis to accommodate reasonable delays in specific screening assessments (eg, PFTs, OCT) due to testing availability. The Medical Monitor must be consulted prior to extension in each case.

Participants may have an abnormal laboratory assessment, repeated 1 time only. If additional retests are considered, the ability to repeat the laboratory assessment should be discussed with the Medical Monitor and the outcome of the conversation should be documented.

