9.3.2. Rescreening

Participants who fail to meet the eligibility criteria can be rescreened per Investigator discretion. Additional screening attempts beyond the first should be approved by the Medical Monitor prior to rescreening. Each participant must be reconsented prior to each screening attempt.

Participants with a Screening visit or Week 0/Day 1 pre-randomization 12-lead ECG showing a second- or third-degree AV block, periods of asystole > 3 seconds, PR interval > 200 ms, or QTcF \geq 450 ms (men) or QTcF \geq 470 ms (women) are not eligible for rescreening.

If a participant requires prophylactic therapy for latent TB, they may be rescreened as outlined in Section 4.2.

If a participant is positive for *C. difficile* at screening, the participant may be treated and retested \geq 4 weeks after completing treatment.

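### Appendix 2 item d sets a four-week prophylaxis threshold for latent TB diagnosed before screening, where exclusion 12 requires a completed course: a minor eligibility inconsistency

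*Protocol*

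**What the plan says.** Exclusion 12 in Protocol Section 4.2, repeated in the synopsis, bars latent TB that is present at screening or was left untreated or poorly treated in the past. It allows two exceptions.

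- The first admits participants with latent TB who "have completed an appropriate course of TB prophylaxis treatment per national/local medical guidelines or WHO guidelines", with active TB ruled out, a clear chest radiograph and no recent close contact with an active case.
- The second concerns "Participants diagnosed with latent TB at screening, ruled out for active TB and received at least 4 weeks of an appropriate TB prophylaxis regimen". These people may be rescreened and finish the course during the trial.

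Appendix 2 covers the same ground in other terms. Item d addresses latent TB diagnosed before screening. It drops the blood or skin test for people with a TB history and states that those with prior latent TB "must have documentation of treatment with at least four weeks of an acceptable TB prophylaxis treatment regimen to qualify for enrollment". Item f addresses a positive test newly found at screening. It calls for screen failure, an evaluation to rule out active TB, prophylaxis begun at least 4 weeks before rescreening, and a plan to complete the course during participation.

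**The concern.** Item d names the very group for which exclusion 12 offers only the completed-course exception, and gives it the shorter threshold that exclusion 12 reserves for a different group. Its treatment sentence does not mention completion.

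Two sites could then decide differently about the same person. One working from Appendix 2 might enrol; one working from Section 4.2 would refuse. A wrong enrolment would be an eligibility violation, and SAP Section 10.2 gives violation of key entry criteria as an example of an important deviation. The study drug lowers lymphocyte counts (Protocol Section 1.3), so TB eligibility should be unambiguous.

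**Working it through.** No arithmetic applies; the check compares the texts case by case.

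| Case | Appendix 2 | Exclusion 12 | Agree? |
|---|---|---|---|
| Diagnosed before screening, course of at least four weeks completed | Item d treatment threshold met | First exception met, if its other conditions hold | Yes |
| Diagnosed before screening, under four weeks taken, unfinished | Item d not met | Neither exception applies | Yes |
| Diagnosed before screening, at least four weeks taken, unfinished | Item d treatment threshold met | First exception fails (not completed); second does not apply (not diagnosed at screening) | **No** |
| First diagnosed at a study screening visit, at least four weeks taken, rescreened | Item f route | Second exception | Yes |

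Only the third row diverges.

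**Which text governs.** Section 4.2 opens with "Participants who meet any of the following exclusion criteria will not be eligible for enrollment into the study". Section 9.1 adds "Protocol waivers or exemptions are not allowed", and Section 9.3 states "Participant eligibility will be assessed based on protocol inclusion and exclusion criteria". On rescreening, Section 9.3.2 says "If a participant requires prophylactic therapy for latent TB, they may be rescreened as outlined in Section 4.2". Exclusion 12 cites Appendix 2 only "for details on TB screening requirements and interpretation of test results", so the appendix does not create a third exception. Exclusion 12 therefore prevails, and the person in the third row is ineligible.

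**Why the wording can still mislead.** Section 9.3.1 and Table 6 footnote e both send sites to Appendix 2 for the TB screening that determines eligibility. Item d links its four weeks to qualifying for enrolment. Unlike item f, its treatment sentence requires neither ruling out active TB nor a plan to finish, so a course taken for four weeks and then abandoned would meet its literal threshold.

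**The case against.** The strongest reply is that item d sets a necessary condition, not a sufficient one. It says what participants must have, whereas item a, for a different group, says outright that they may enrol. On that reading four weeks is a floor, exclusion 12 applies on top, and a site can satisfy both. The floor even has a use: a rescreened person has latent TB diagnosed before that second screening, and four weeks is the right minimum for them.

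Safeguards also exist. Item d has the investigator verify the adequacy of previous treatment, item e ties acceptable regimens to local or WHO guidelines, and item g requires an expert to assess both the regimen and its duration. Table 6 schedules the eligibility check at screening and again on Day 1, and Section 9.4.1 allows only those still meeting all criteria to be randomized.

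Much of this stands. The floor reading is possible and the safeguards lower the risk. But item d does not say that it is a floor, and it does not separate rescreened people from those diagnosed before any contact with the study. For the latter, a four-week floor adds nothing to a completed-course rule. None of the safeguards in Appendix 2 names completion as the standard.

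A reader might infer more than the documents support:

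- **That Appendix 2 overrides exclusion 12.** It does not, for the reasons given in the working.
- **That a safety gap has been shown.** Exclusion 12 itself accepts an unfinished course in rescreened people, and Section 5.1 requires discontinuation for confirmed active TB.
- **That the efficacy results are affected.** The Per Protocol Set is supplementary (SAP Sections 3.3 and 5.4) and no statistical test is planned (SAP Section 6.5).
- **That anyone on prophylaxis at first dose was wrongly enrolled.** The second exception permits exactly that.

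**Conclusion.** Item d is wrong as written, as a minor eligibility inconsistency. It states a four-week threshold for a group that exclusion 12 admits only after a completed course.

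The size cannot be quantified, because the documents give no number of participants with prior latent TB. The documents do not show that anyone was wrongly enrolled.

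The conclusion assumes that an unfinished course begun before the study counts as latent TB at screening, or as inadequately treated, so that an exception is needed. It also takes diagnosis at screening to mean a screening visit for this study. Both are the natural reading of exclusion 12, but the protocol does not spell them out.

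**What to change.** Replace the treatment sentence in item d with two:

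1. Latent TB diagnosed before the first screening visit for this study requires documentation of a completed acceptable prophylaxis course, as in exclusion 12.
2. People first diagnosed at a study screening visit and rescreened under item f and the second exception still qualify with at least four weeks, active TB ruled out and a plan to complete the course during the trial.

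If the sponsor meant four weeks to suffice for all latent TB, exclusion 12 should be amended instead, in Section 4.2 and the synopsis, with the same conditions. Aligning item d costs two sentences and loses no eligible participant, since those affected are already barred.

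SAP Sections 3.1 and 7 say that the study is being stopped early. If enrolment has closed, the edit is moot and only a check remains. It belongs within the deviation review in SAP Section 10.2, which already has an eligibility category. Look for enrolled participants whose prophylaxis began before their first screening consent and was unfinished at first dose. Use the start dates on the TB questionnaire and in the medication records.

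Three limits apply:

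- The questionnaire asks for an expected stop date and no diagnosis date. Starting before first consent is therefore a proxy, and it misses anyone diagnosed earlier who began treatment only after consenting.
- Protocol Section 9.3.5 requires medication records only for the 30 days before first dose and for ongoing drugs. Courses that ended earlier need the site's treatment documents.
- The listing of exclusion criteria met (SAP Section 10.1) helps only if the site recorded the case as an exclusion.

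Apart from those site documents, the check uses data already collected.
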